 - Gleason score $> 4+3=7$
 - Extracapsular spread.
 - Nodal or distant metastasis
 - Contraindications to MRI or general anesthesia.
 - Uncorrectable Coagulopathy.
 - Refusal of participation.
 - Lesions not visualized on the multiparametric MRI

Recruitment Goal:

A total of 20 subjects will be targeted for recruitment to this study.

Intervention:

- **Equipment used in the study:**

- For transrectal approach:
 - Siemens MRI scanner, 3 Tesla, 32 channel surface coil is used. No endorectal coil.
 - DynaTRIM needle holder/targeting system for transrectal guidance
- For Transgluteal approach:
 - Siemens MRI scanner, 1.5 Tesla.
- A 980 nm diode laser system (Visualase Inc.)

- **Pre-intervention investigations:**

All patients will be subjected to the following:

- *Lab tests:*

- Baseline Serum prostatic specific antigen (PSA).
- Baseline urine analysis.
- INR and platelet count.

- *Imaging:*

- Multiparametric MRI (mpMRI), including high resolution T2WI, diffusion weighted imaging (DWI), dynamic contrast enhanced (DCE) MRI.
- *Targeted In-bore MRI guided biopsy for suspicious lesions in mpMRI as well as to apparently normal areas to exclude possibly of occult clinically significant tumors (in subjects with limited visible disease).*
- *Baseline QOL questionnaires.*

- **Procedure:**

Patient preparation:

- ✓ *Before coming to the hospital:*

- Oral Antibiotics (Fluoroquinolone) for 7 days, starting one day before procedure.
- Oral Urinary tract analgesic (Phenazopyridine) for 5 days.
- Stop anticoagulants for 5 days before the procedure.
- Fasting for at least 8 hours the night before the procedure.
- Bowel preparation: Fleet enema on the morning of the ablation.

✓ *At the hospital*

- A Foley catheter will be placed to protect the urethra during and following the ablation procedure. This will be removed by the interventional MRI program's nurse after 3 days.

Ablation procedure:

- Patient position: Prone
- Anesthesia: general.
- Laser fiber placement will be performed by one of two approaches based on the target location within the prostate gland:
 - Transgluteal:
 - A 14-gauge MR compatible co-axial puncture needle will be introduced into the target lesion via a transgluteal approach under real-time MR fluoroscopy guidance.
 - Transrectal:
 - The rectal piece of the Dyna-TRIM system will be inserted following lubrication with lidocaine gel.

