- Urinary tract obstruction.

- **Outcome:**

Primary endpoint:

- Treatment Efficacy: measured by recurrence rate at 1-year post-ablation (i.e. number of recurrences/number of subjects).

Secondary endpoint:

- Recurrence rate at two-year post ablation time point.

**recurrences are defined as any newly developed mpMRI abnormality contiguous with the ablation zone and proved by subsequent targeted biopsy.

- Methods of assessment (each follow up visit):
 - Mp-MRI scans with each follow up visit:
 - Ablation zone: assessed for residual tumor.
 - Non-ablated areas: for new tumor(s).
 - MRI guided biopsy for the ablation site after one and two years or if a suspicious lesion developed during follow-ups.
 - Serum PSA.
- Safety and functional outcomes:

- Complications: Grade 3 complications or higher as defined as National cancer institute's common toxicity criteria version 4: *incontinence or urinary retention necessitating surgical intervention or new-onset erectile dysfunction not responsive to medication.*
- *Urinary function* → will be assessed by IPSS at baseline pre-ablation visit and with each follow up visit.
- *Erectile function* → will be assessed by SHIM baseline pre-ablation visit and with each follow up visit.
- Other Procedural complications: Infection, bleeding, hematuria, fistula.

Participant timeline:

**Each follow up time point is calculated from the previous visit, not from procedure date

Recruitment strategy:

- We will rely on either physician referral or self-referral.
- Self-referred subjects will be counseled about standard of care treatment options. For these subjects, the study team will document evaluation by a radiation oncologist for each participant and decline of the recommended modality.
- No financial incentives will be offered.

- Posting basic descriptive information on ClinicalTrials.gov

Informed consent:

- Informed consents will be obtained in person on 1st visit in a private room.
- Subjects will be allowed time to discuss with others before deciding to enroll.
- The study process and details will be discussed verbally with the patients.
- Time will be allowed for questions.
- A hand-out will be provided to the patients with frequently asked questions.

Data collection & management:

- All patients' data will be documented in the electronic medical records (powerchart) through the standard clinical process.
- All treatment-related hard copy documents will be scanned into the electronic medical records (powerchart).

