The primary endpoint is the recurrence rate at 1 year, defined as the number of recurrences divided by the number of patients. For this study, Simon's two-stage design will be utilized, using the Minimax design. (25, 26) The null hypothesis that the true recurrence rate is 0.49 will be tested against a one-sided alternative. In the first stage, 18 patients will be accrued. If there are 6 or more recurrences in these 18 patients, the study will be stopped. Otherwise, 2 additional patients will be accrued for a total of 20. The null hypothesis will be rejected if 6 or fewer recurrences are observed in 20 patients. This design yields a type I error rate of 0.05 and power of 0.8 when the true recurrence rate = 0.22.

Recurrence rate at 1 year, as well as at follow-up visits at 3 weeks, 3 months, 6 months, and 2 years will be estimated, and exact 95% confidence intervals will be estimated using the Clopper-Pearson method (27). Number of complications and rate of complications will be summarized using frequencies and percentages. Additionally, all numeric patient characteristics will be summarized using mean, standard deviation, median,

and range, and all remaining categorical patient characteristics will be summarized using frequencies and percentages. No loss to follow-up is expected.

Erectile function and urinary function will be summarized at baseline and at each follow-up visit using Quality of Life (QoL) assessments – SHIM for erectile function and IPSS for urinary function. Scores will be aggregated across questions, and grouped into ordinal categories. For each QoL measurement, frequencies and proportions of each ordinal category will be reported at baseline and at each follow-up visit. To assess the measurements longitudinally, we will consider an ordinal logistic regression model using a generalized estimating equations (GEE) approach for handling correlation within patients in order to evaluate the impact of time on erectile and urinary function.

Stopping rules for safety are detailed in the DSMP section below.

Data and safety monitoring plan (DSMP):

The PI will ensure that the protocol is conducted in a consistent manner and that all PHI from the study obtained is handled in a HIPAA compliant manner.

1. Monitoring the Progress and Safety of the Trial

a. What are the potential risks and benefits for study participants?

Risks:

- Urinary tract infection, sepsis
- Hematuria
- Urinary retention
- Erectile dysfunction
- Urinary incontinence

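### SHIM and IPSS are reported and modelled only as ordinal categories, so change within a category is lost and no change from baseline is estimated on the score scale

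*Combined protocol and SAP*

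**What the plan says.** The Statistical analysis plan treats SHIM and IPSS alike: "Scores will be aggregated across questions, and grouped into ordinal categories". It then provides for two things: counts and proportions in each category at baseline and at each follow-up, and an ordinal logistic GEE for the effect of time. The model is worded tentatively, as something to be considered. The number of categories and the cut-offs are not stated. The mean, SD, median and range are promised for numeric patient characteristics, not for functional scores over follow-up.

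The totals will exist. Under Outcome, urinary function "will be assessed by IPSS at baseline pre-ablation visit and with each follow up visit", and SHIM follows the same schedule. Data collection & management lists both at baseline and at each follow-up.

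The sample is small: "A total of 20 subjects will be targeted for recruitment to this study". The plan also says: "No loss to follow-up is expected". The background section lists functional outcome (safety) as the first of two trial goals. Under Outcome, however, only recurrence is named as a primary or secondary endpoint, and the plan states no test level or power for SHIM or IPSS.

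**The concern.** Once a total is replaced by its category, movement inside the category disappears. With IPSS cut-offs at 8 and 20 (assumed here), a patient who goes from 8 to 19 has worsened by 19 − 8 = 11 points and counts as unchanged. A patient who goes from 7 to 8 has worsened by 1 point and counts as a category shift.

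What is at stake is the first-listed goal. The rationale for focal treatment is that it spares function, and the background section cites small earlier studies for having found no significant change in quality of life. With 20 patients and a coarse outcome, a non-significant time effect is easier to reach even when function has declined. The plan offers no score-scale estimate with an interval to show how much decline the data leave open.

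**Working it through.** **1. The plan's own power statement.** The only one concerns 1-year recurrence. The inputs from the Statistical analysis plan are "The null hypothesis that the true recurrence rate is 0.49 will be tested against a one-sided alternative", "If there are 6 or more recurrences in these 18 patients, the study will be stopped" and "The null hypothesis will be rejected if 6 or fewer recurrences are observed in 20 patients". The probability of rejecting is the sum over x = 0 to 5 of P(X₁ = x) × P(X₂ ≤ 6 − x), with X₁ ~ Bin(18, p) and X₂ ~ Bin(2, p).

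- p = 0.49: 0.0481 (stated 0.05)
- p = 0.22: 0.8049 (stated 0.8)

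The stated figures reproduce. They do not involve SHIM or IPSS, so nothing below affects them.

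**2. Inputs for the functional scores.** From the documents: n = 20 with no loss to follow-up. Everything else is assumed: a 3-point worsening from baseline to one visit; correlation ρ of 0.5 or 0.7; two-sided 5% level; an IPSS-like score of 0–35 with mean 10, SD 6 and cut-offs 8 and 20 (3 categories); and a SHIM-like score in 5 categories.

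**3. Closed-form check on the totals (IPSS-like).** The standardised change is d = δ / (σ√(2(1 − ρ))), and paired-t power comes from the noncentral t with 19 df and noncentrality d√20.

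- ρ = 0.5: d = 3 / (6 × 1) = 0.50; noncentrality 2.24; power 0.565
- ρ = 0.7: d = 3 / (6 × 0.775) = 0.645; noncentrality 2.89; power 0.782

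These agree with the simulated 57% and 78% in the next table.

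**4. Power on totals against power on categories.** Comparison A sets a paired t-test on totals against an ordinal GEE on categories (3,000 runs per setting). Comparison B uses the same paired test on both scales, so that only the scale differs.

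| Score | ρ | A: totals → categories | A: loss | B: totals → categories | B: loss |
|---|---|---|---|---|---|
| IPSS-like, 3 categories | 0.5 | 57.2% → 36.7% | 20.5 | 55% → 36% | 19 |
| IPSS-like, 3 categories | 0.7 | 78.3% → 46.1% | 32.2 | 77% → 44% | 33 |
| SHIM-like, 5 categories | 0.5 | 71.0% → 67.6% | 3.4 | 71% → 65% | 6 |
| SHIM-like, 5 categories | 0.7 | 90.5% → 84.6% | 5.9 | 90% → 81% | 9 |

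B was repeated with 40,000 runs, integer scores, and for SHIM an assumed mean of 18, SD 5 and cut-offs 8, 12, 17 and 22. The losses were 20.8 and 33.9 points (IPSS-like) and 6.9 and 8.3 points (SHIM-like). Because B shows much the same loss as A, the loss comes from the categories and not from switching tests. In A, the ordinal test's type I error was 5.8–7.1%, so its power is, if anything, slightly flattered.

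**5. How far the answer moves with the assumptions.** With the effect set so that the total has 80% power (d = 0.66, n = 20) and ρ from 0.5 to 0.85, the loss in points on the categories is:

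| Categories | Centred cut-offs | Off-centre cut-offs |
|---|---|---|
| 7 | 6–12 | 24–31 |
| 5 | 8–18 | 30–39 |
| 3 | 17–36 | 46–57 |

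A check of GEE on the total against ordinal GEE on the category (200 runs per scenario) gave losses of about 6–18 points (5 categories) and 25–72 points (3 categories) with one follow-up. With six time points the losses were about 2–12 and 10–42. Two cautions apply. Power on the total was already 95% or more in the six-time-point runs, so part of that shrinkage is a ceiling effect. Also, up to 15 of 200 ordinal fits gave no p-value in some 3-category scenarios and were counted as non-significant, which explains only a small part of the loss. In a wider paired-test grid the loss fell to between 0 and 0.5 points where the true change was large.

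**The case against.** Several points on the other side stand. SHIM and IPSS are not named endpoints, and they carry no hypothesis, test level or power target. The ordinal model is only to be considered. An ordinal model is a legitimate choice for bounded scores in 20 patients, since mean change assumes equal spacing and is affected by floors and ceilings. Category tables at each visit would still show patients who cross a cut-off. The planned model uses all visits, so a comparison of baseline with one visit is not the planned analysis, and the six-time-point losses were smaller.

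Stronger readings are tempting but are not supported:

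- A reader might infer that categorising costs a definite amount, say up to 30 points of power. No such figure can be derived from these documents, and 30 is not a ceiling: assumed settings give anything from near zero to more than 50.
- A reader might infer that the analysis is biased towards no change. Lower power is not estimator bias, and the simulated ordinal test rejected slightly too often, not too rarely, when there was no change.
- A reader might infer that the trial sets out to prove that function is preserved. The text says only that functional outcomes will be evaluated, and no rule equates non-significance with preservation.
- A reader might infer that the main result is weakened. The recurrence test does not use these scores.

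None of this answers the remaining gap: the totals will be available, and no change in them is to be estimated.

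**Conclusion.** The point holds as a loss of sensitivity in a supportive safety analysis. Following the plan as written yields no score-scale change and no interval for it, and the categories themselves are undefined, so cut-offs could be chosen after the data are seen. Under the stated assumptions (3-point worsening, one follow-up, ρ 0.5–0.7, n = 20), the loss is about 3–9 points of power for a SHIM-like score in 5 categories and about 20–34 for an IPSS-like score in 3. Only the sample size and the absence of loss to follow-up come from the documents, so the direction is firm and the size is illustrative. The recommendation does not depend on any one power figure.

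**What to change.** Amend the functional-outcome paragraph of the Statistical analysis plan as follows:

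- Make change from baseline in total SHIM and total IPSS the main longitudinal analysis. Use a mixed model or a GEE on the total score, with visit as a factor and a small-sample correction. Name one of the two in advance. The simulated gains above are for a paired t-test and a GEE on totals; a mixed model was not simulated.
- Report mean or median change with a 95% CI at each visit, with 1 year as the main time point. Giving the median as well covers floor and ceiling effects.
- State the category cut-offs for both instruments before any follow-up data are examined. Keep the category frequencies as descriptive tables and the ordinal GEE as supportive, if wanted.
- State that a non-significant time effect will not by itself be read as preserved function, and that the interval will be used instead. For illustration, with SD 6 and ρ = 0.5 the SD of change is 6, and the 95% half-width at n = 20 is 2.093 × 6 / √20 = 2.8 points.

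This is a free improvement. It changes SAP wording only and needs no new data, visits or patients.

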The DSMC will review pertinent aspects of the study to assess subject safety, compliance with the protocol, data collection, and risk-benefit ratio. Specifically, the Winship Cancer Institute Internal Monitors assigned to the DSMC may verify informed consent, eligibility, data entry, accuracy and availability of source documents, AEs/SAEs, and essential regulatory documents. Following the monitoring review, monitors will provide a preliminary report of monitoring findings to the PI and other pertinent individuals involved in the conduct of the study. The PI is required to address and respond to all the deficiencies noted in the preliminary report. Prior to the completion of the final summary report, monitors will discuss the preliminary report responses with the PI and other team members (when appropriate). A final monitoring summary report will then be prepared by the monitor. Final DSMC review will include the final monitoring summary report with corresponding PI response, submitted CAPA (when applicable), PI Summary statement, and available aggregate toxicity and safety data.

The DSMC will render a recommendation and rating based on the overall trial conduct. The PI is responsible for ensuring that instances of egregious data insufficiencies are reported to the IRB. Continuing Review submissions will include the DSMC recommendation letter. Should any revisions be made to the protocol-specific monitoring plan after initial DSMC approval, the PI will be responsible for notifying the DSMC of such changes. The Committee reserves the right to conduct additional audits if necessary.

Internal monitoring:

The PI for the study, [name] in the Department of Radiology and Imaging Sciences will ultimately be responsible for monitoring the trial. The study coordinator will ensure that all protocol elements are implemented as proposed. This will be in conjunction with other members of the study team and various co-investigators. An internal monitoring committee of the study team will meet every 3 months to review quality and safety data related to the trial. The information that would be reviewed are number of UPs (defined below in #2), the type of UP, a review of the response to the UP and its effect on patient outcome, and an analysis of what could have been done to prevent the UP.

e. What are the stopping rules for the study?

The stopping rule will be: Three or more Grade 1 or Grade 2 UPs, or greater than two Grade 3 UPs in one 3-month period.

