In case of testing a new MRI pulse sequence during these procedures, we will observe for any unexpected hazards related to noise effect or skin heating.

f. What procedures are in place for multicenter trials, if applicable?

N/A. This is a single center trial.

g. How will conflict of interest, or the perception of a conflict, be managed?

The study team, including individuals obtaining consent from the patient to participate in the study, have no financial or other interest in whether or not the patient participates. MRI's will be conducted only on patients who require a clinically indicated MRI, who have no additional contraindications to MRI, and who do not meet other exclusion criteria as outlined above.

2. Reporting of Unanticipated Problems (UPs)

a. What constitutes a UP (include a definition, grading scale, and “study relatedness” criteria)?

UP: A problem not expected to be encountered during the course of the typical clinical policy and protocol used for performing MRIs in patients having an interventional procedure.

Grade 1: Auditory disturbances or skin erythema related to testing new pulse sequences.

Grade 2: Skin burn or a significant change in vital signs requiring the interventional procedure to be aborted, when these changes are related to testing new pulse sequences.

Grade 3: Patient death

UPs not specifically related to the study (MRI is performed in these patients for a clinically indicated reason and in accordance with a standard clinical protocol), will not be reported to the IRB but will rather be reported through the regular clinical pathways.

b. What is the process for assuring that UPs are reported appropriately?

All UPs (grade 2 and 3) will be reported directly to the study PI and logged at the MRI console by the MRI technologist. The study PI will be responsible for reporting UPs to the IRB.

c. What are the timelines for UP collection and reporting?

UPs will be collected as they occur, and promptly reported to the IRB, as appropriate.

3. Reporting of Suspensions or Terminations

a. Which actions (FDA, Sponsor, IRB, etc.) will be reported and who insures these actions are reported appropriately?

All Grade 2 and 3 UPs will be reported to the IRB. The study PI will insure these are reported appropriately. There are no sponsors of this study.

4. Assuring Data Accuracy and Protocol Compliance

a. How are data accuracy and protocol compliance assured?

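### The only written safety stopping rule counts lower-grade problems and deaths separately, so a more severe mix of events can miss a stop that a milder set of the same size triggers

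*Combined protocol and SAP*

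**What the plan says.** The Statistical analysis plan contains no safety boundary of its own and hands the matter over: "Stopping rules for safety are detailed in the DSMP section below". The early stop that it does describe, in the two-stage design, concerns recurrence.

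Item 1e of the Data and safety monitoring plan (DSMP) gives the rule: "Three or more Grade 1 or Grade 2 UPs, or greater than two Grade 3 UPs in one 3-month period".

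Item 2a supplies the grades:
- The mildest category is hearing trouble or reddened skin linked to a new sequence under test.
- The middle category, which likewise counts only when it is linked to a new sequence under test, reads: "Grade 2: Skin burn or a significant change in vital signs requiring the interventional procedure to be aborted".
- The most severe category carries no such link and consists of one event: "Grade 3: Patient death".

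Other oversight exists without a numeric trigger. Under item 1d an internal committee of the study team meets every three months and reviews UPs. DSMC review takes place every six months or annually, depending on risk level: "The DSMC will render a recommendation and rating based on the overall trial conduct". Under items 2 and 3, Grade 2 and Grade 3 UPs go to the IRB.

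**The concern.** A stopping rule for harm should respect severity: if a set of events is bad enough to stop the study, replacing one of them with something worse should not take the stop away. Item 1e does not guarantee this. A Grade 3 UP adds nothing to the Grade 1/2 count, a Grade 1/2 UP adds nothing to the Grade 3 count, and no sentence says how a mixed set is to be judged.

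The Statistical analysis plan relies on this rule alone for safety stopping. In a mixed-grade case, those applying it as written would have no instruction to stop, although the same number of milder events would have required one. The decision would then rest on judgement in a situation where a written rule is meant to settle it.

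**Working it through.** The plan states no operating characteristics for this rule, so there is no figure to reproduce. The check is a full enumeration.

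**Inputs.** Let L be the number of Grade 1 or Grade 2 UPs and D the number of Grade 3 UPs (deaths that qualify as UPs) within one three-month window. The thresholds come from item 1e and the grades from item 2a.

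**Rule as written.** Stop if L ≥ 3 or D > 2. Because D is an integer, D > 2 is the same as D ≥ 3. Each limb therefore needs three events of its own kind, and a death moves the study no nearer to stopping than an episode of erythema does.

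**All patterns by total number of UPs, written (L, D).**

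| Total | Rule met | Rule not met |
|---|---|---|
| 0 to 2 | none | all |
| 3 | (3,0), (0,3) | (2,1), (1,2) |
| 4 | (4,0), (3,1), (1,3), (0,4) | (2,2) |
| 5 or more | all | none |

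The rule is not met exactly when L ≤ 2 and D ≤ 2, which is 3 × 3 = 9 patterns. Three of the nine contain three or more UPs: (2,1), (1,2) and (2,2). The largest holds 2 + 2 = 4 UPs, two of them deaths.

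**The reversal.**
- Three erythema events, or three skin burns, tied to a new sequence: L = 3, rule met.
- Change one of three burns to a death: L = 2 < 3, and D = 1 is not > 2, so the rule is not met.
- Change a second one: L = 1, D = 2, not met.
- Four burns meet the rule. Change two of them to deaths: L = 2, D = 2, not met.

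**Sensitivity to wording.**
- If Grades 1 and 2 are counted separately rather than pooled, the three mixed patterns still fail to meet the rule.
- It is unclear whether the three-month window governs the first limb as well as the second. If the first limb runs over the whole study, the examples come out the same within a window, provided no Grade 1/2 UP occurred earlier.

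**The case against.** **Reach.** Grade 1 and Grade 2 UPs exist only when a new pulse sequence is being tested. The DSMP treats such testing as a possibility, and the procedure description names no sequence as new. If none is tested, L is always 0 and the three patterns cannot occur. Even if one is tested, the patterns need sequence-related UPs and at least one qualifying death in the same window, in a small trial: "A total of 20 subjects will be targeted for recruitment to this study". This stands, and it limits how much weight the point carries. A reader might also take the burns for laser-ablation injuries; item 2a does not support that.

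**Other oversight.** A reader might infer that treatment would in fact go on after deaths. The documents do not support that either. What follows is only that the written rule is not triggered. The IRB, the DSMC and the internal committee could each halt the study. None has a stated numeric trigger, however, so this reduces the consequence without repairing the rule.

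**A charitable reading.** The first limb could be meant as Grade 1 or worse. The Outcome section adds wording to that effect when it defines complications of Grade 3 and above; item 1e has none. At best the rule is ambiguous, and that also needs correcting.

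**What the defect is not.** Adding an event never undoes a stop, because the rule is monotone in each count taken alone. The reversal appears only when a lower-grade event is replaced by a death. It is also tempting to attach a probability to a missed stop, but the documents give neither a UP rate nor the share of UPs that would be deaths, so none can be supported. Finally, two deaths with no other UP also leave the rule unmet. That follows from the count in the second limb, which is a separate question.

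**Conclusion.** The point holds. As written, item 1e is met by three Grade 1 or Grade 2 UPs but not by (2,1), (1,2) or (2,2), so it is not monotone in severity. This follows from the wording of items 1e and 2a alone and needs no assumed event rate.

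Its size is three count patterns, expected to be rare in 20 subjects and possible only if a new sequence is tested. It rests on reading the limbs literally, as separate counts. It merits correction because no other safety stopping rule is written and the plan gives no reason for treating mixed grades this way.

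**What to change.** The PI, together with the DSMC, should reconcile the stopping rule in DSMP item 1e with the UP grades in item 2a. Item 1e should state how UPs of different grades combine within a period, with one property guaranteed: a more severe set of events can never fail to trigger a stop that a milder set of the same size triggers. The thresholds are for the PI and the DSMC to set; none is proposed here.

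Two clarifications belong in the same edit. Item 1e should say whether the three-month window applies to both limbs. Item 2b should make clear how Grade 1 UPs enter the count, since the logging route it describes covers only the higher grades: "All UPs (grade 2 and 3) will be reported directly to the study PI and logged at the MRI console".

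The cost is a short change of protocol wording, with notice to the DSMC. It needs no new event definitions, since the rule already uses UPs of every grade. The downside is that the rule could be met in a few mixed-grade patterns where it now is not.

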- Fecal incontinence
- Bleeding per rectum
- Recto-ureteral fistula
- Urinary tract obstruction.
-

The benefit to the patient is receiving a standard treatment protocol with the possibility of extra imaging which may enhance the diagnostic ability of the physician. Subject participation may help future patients having this same procedure.

b. What is the screening process and how it will be used to protect participants?

MRI scans will be conducted only on patients who require a clinically indicated MRI as determined by a urologist and/or a radiologist, who have no additional contraindications to MRI, and who do not meet other exclusion criteria for MRI. When the patient arrives for MRI (or if seen earlier at the interventional MRI clinic as a part of pre-procedure evaluation), he will undergo routine screening to ensure the absence of any incompatible implants or devices, screening and consent for intravenous contrast (if clinically indicated) making sure there are no contraindications to contrast if contrast is indicated.

c. What are the measures to protect participants against risk?

Patients will be initially counseled about the current standard of care treatments available and that the study procedure is experimental. The study team will document evaluation by a radiation oncologist for each self-referred participant and decline of the recommended modality.

Proper identification of cancerous lesion(s) will be performed with pre-treatment multiparametric MRI to assess the technical appropriateness of MRI guided focal laser ablation. Prior to starting the ablation procedure, normal saline may be infused into the recto-prostatic space (hydro-dissection) to protect the rectum from injury during ablation if that process is deemed necessary on pre-procedure imaging. Subjects undergoing the treatment procedures will benefit from real-time monitoring with temperature maps and damage estimate maps performed online as the ablation procedure is being conducted. Additionally, an immediate post-procedure new baseline MRI of the prostate will be performed before the subjects leaves the MRI unit. This will also be used to evaluate for and manage any immediate complications.

Procedures will be performed on an out-patient same-day surgery basis. Subjects will recover in the standard recovery area and discharged on the same day unless a complication occurs.

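### The only pre-specified safety stopping rule counts MRI pulse-sequence effects and deaths: no listed non-fatal ablation complication can trigger it, and two deaths in three months do not meet it

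*Combined protocol and SAP*

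**What the plan says.** The Statistical analysis plan section sets no safety boundary of its own and points to the DSMP. DSMP 1e states a single rule: "Three or more Grade 1 or Grade 2 UPs, or greater than two Grade 3 UPs in one 3-month period".

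DSMP 2a defines what is counted. A UP is a problem that would not be expected in the usual conduct of MRI for interventional patients. The grades are:

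- "Grade 1: Auditory disturbances or skin erythema related to testing new pulse sequences"
- Grade 2: a skin burn, or a vital-sign change serious enough to abort the procedure, but only "when these changes are related to testing new pulse sequences"
- "Grade 3: Patient death"

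DSMP 1a lists nine risk entries for participants, from "Urinary tract infection, sepsis" through retention, erectile dysfunction, incontinence and rectal bleeding to "Recto-ureteral fistula" and urinary obstruction. The Outcome section separately defines complications of NCI version 4 Grade 3 or higher as a safety outcome. The SAP only summarizes complications as frequencies and percentages, and neither section links them to stopping.

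**The concern.** Safety is half of the stated study objective, and DSMP 1c has patients told that the procedure is experimental. A safety stopping rule should respond to harm from the treatment under test. This one responds to the scanner and to death. Sepsis, a fistula or incontinence needing surgery has no UP grade, so a team that follows DSMP 1e exactly has no stated trigger for serious non-fatal harm from the ablation.

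The thresholds also run the wrong way. Three mild skin reactions stop the trial, while two deaths within three months leave it open.

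The other pre-specified stop does not help. It is the first-stage recurrence rule, which concerns efficacy and applies after 18 of the 20 patients.

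**Working it through.** The documents give no operating characteristic for the safety rule, so there is no stated figure to reproduce. The main result is a matter of definitions and needs no assumed rate.

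**Step 1: match events to the rule**

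| Event | Grade in DSMP 2a | Can it count under DSMP 1e? |
|---|---|---|
| Erythema or auditory effect of a new pulse sequence | 1 | Yes; three suffice |
| Burn or aborting vital-sign change from a new pulse sequence | 2 | Yes; three suffice |
| Unstable vital signs from sepsis or bleeding | None (not due to a pulse sequence) | No |
| Any of the nine DSMP 1a entries, non-fatal | None | No |
| Two deaths in three months | 3 | Not met; more than two means at least three |

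So 0 of the 9 listed entries can trigger the rule when non-fatal, even if all 20 patients were affected. Grade 3 in the rule cannot be read as NCI Grade 3, because the rule counts UPs and DSMP 2a gives UPs their own scale. It is unclear whether the 3-month window applies to both limbs; the result is the same either way.

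**Step 2: the death limb, with assumed rates**

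Let X ~ Binomial(20, p), with 20 the recruitment goal and p an assumed procedure-death rate.

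- P(X ≥ 3) = 1 − Σ C(20, x) pˣ (1 − p)²⁰⁻ˣ over x = 0, 1, 2. At p = 0.05: 1 − (0.3585 + 0.3774 + 0.1887) = 0.075. This is an upper bound on the rule triggering, because requiring the deaths to fall within three months can only lower it.
- P(X ≥ 1) = 1 − (1 − p)²⁰. At p = 0.01: 1 − 0.99²⁰ = 0.18.

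| Assumed death rate | Three or more deaths in 20 | First death |
|---|---|---|
| 1% | 0.001 | 0.18 |
| 2% | 0.007 | 0.33 |
| 5% | 0.075 | 0.64 |

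**Step 3: what a complication limb would do (illustration only)**

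Take three Grade 3+ complications in 20 patients as the limit, and let T be the number of the patient with the third event. A stop spares at least one patient if T < 20 when each event is known before the next treatment. If five more patients are treated first, it does so if T + 5 < 20. Equivalently, at least three events must fall in the first 19 or the first 14 patients.

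| Assumed Grade 3+ rate | Limit reached in 20 | Spares ≥ 1, no delay | Spares ≥ 1, five-patient delay | Rule as written |
|---|---|---|---|---|
| 5% | 0.075 | 0.07 | 0.03 | 0 |
| 10% | 0.32 | 0.29 | 0.16 | 0 |
| 20% | 0.79 | 0.76 | 0.55 | 0 |
| 30% | 0.96 | 0.95 | 0.84 | 0 |

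The last column is for non-fatal events.

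**Step 4: what prior data exclude**

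The Background reports no complications in the site's 14 cases. The exact two-sided 95% upper limit is 1 − 0.025^(1/14) = 0.232. Adding the 8-patient phase I trial that saw no major complications gives 0/22 and 1 − 0.025^(1/22) = 0.154. The pooling assumes comparability and mixes any complication with major complications, so it is only a rough guide.

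**The case against.** The strongest reply is that DSMP 1e is not the only safeguard. The DSMC assesses subject safety and risk-benefit, its monitors may check adverse events, it sees aggregate toxicity data, and it issues a recommendation that goes into continuing review. "The Committee reserves the right to conduct additional audits if necessary". For the IRB route, "UPs will be collected as they occur, and promptly reported to the IRB, as appropriate", so a study-related death should reach the IRB well before a third. The institutional monitoring plan cited in DSMP 1d is not part of these documents and may contain thresholds. The internal committee meets every three months with a general remit over quality and safety data.

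All of this stands as mitigation, and it means that one cannot say no trigger exists anywhere. It does not supply a stated one. DSMC review is six-monthly or annual and has no complication limit here, and the information itemized for the internal committee is UPs only. Whether a death from ablation or anesthesia would count as a UP is itself uncertain, since the definition concerns MRI and problems not specific to the study go to clinical pathways. That makes the death limb weaker, not stronger.

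Two further objections are fair. The rates in the tables are assumed. The benefit of a 3-in-20 limit is also modest when events surface late: with a 10% rate and a five-patient delay, an average of 19.29 of 20 patients would still be treated. This argues for choosing the limit with care. It does not justify a rule that cannot react at all.

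**Conclusion.** The concern holds and must be fixed. Followed exactly, the stated rule gives the wrong result: it cannot react to any non-fatal ablation complication on the protocol's own risk list, and it tolerates two deaths in three months while stopping for three erythemas. Confidence in this is high, because it follows from the definitions alone.

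The probabilities show only the practical size and depend on the assumed rates, on independence between patients and, for the delayed case, on an assumed lag of five patients. The prior experience is reassuring but too small to make a rule unnecessary: zero of 14 is compatible with a complication rate of up to 23.2%. The statement that serious non-fatal harm has no stated trigger is limited to the documents at hand.

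**What to change.** Rewrite DSMP 1e and 2a so that the rule counts:

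- any death possibly related to the procedure, with a single death pausing accrual until the DSMC has reviewed it;
- all treatment-related complications of NCI version 4 Grade 3 or higher. Infection or sepsis, bleeding and fistula, which the Outcome section lists apart from the graded complications, should be expressly included alongside incontinence, retention and erectile dysfunction.

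The DSMC should agree the limit for the second item; 3 in 20 is only an illustration. Pulse-sequence events can stay as a separate item. The 3-monthly internal committee should review the graded complications as well as UPs. Complication grade, including late infection, bleeding and fistula, should be added to the follow-up items under Data collection & management, which now list immediate complications only under the procedure data.

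The cost is a protocol and DSMP amendment with DSMC agreement, one added data field and a possible accrual pause. With the illustrative limit, that limit would be reached with probability 0.075 if the true Grade 3+ rate were 5%. No visits are added: SHIM, IPSS and continence are already collected at each follow-up, and obstruction or leak is checked at catheter removal.
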